### ECG Abnormalities

If a clinically significant finding is identified (including but not limited to changes from baseline in QTcF after enrolment), the Investigator or qualified designee will determine if the participant can continue in the study and if any change in participant management is needed. This review of the ECG printed at the time of collection must be documented. Any new clinically relevant finding should be reported as an AE.

When the following ECG change conditions are met, study treatment **MUST** be discontinued, the DCC and study PI informed, and further steps discussed:

- Absolute QTcF >500 ms or >60 ms increase from baseline as confirmed with 3 consecutive ECGs taken in a 30-minute period with at least 5 minutes between each ECG. The mean of the 3 ECGs will be used for decision making.

### Other Laboratory Parameters

Study treatment **MUST** be discontinued if the following laboratory parameters criteria are met:

- Absolute neutrophil count less than or equal to  $1.0 \times 10^9/L$  on 2 consecutive repeat tests within 48 to 72 hours.

### Other

Study treatment **MUST** be discontinued if the following other criteria are met:

- Significant safety issues (as judged by the Site Investigator). This includes AEs considered unacceptable by the patient and/or the Investigator
- Any other protocol deviation that results in a significant risk to subject's safety
- Pregnancy as confirmed by positive urine test at any time during the study
- Withdrawal of informed consent

Participants may voluntarily discontinue investigational treatment for any reason at any time. Participant decision on discontinuation of study treatment does not imply an automatic withdrawal from the study.

Refer to the Schedule of Activities (SoA) for data to be collected at the time of treatment discontinuation and follow-up and for any further evaluations that need to be completed.

### 8.1.1. Temporary Discontinuation

Study treatment dosing may be temporarily suspended in the event of:

- Clinically important laboratory abnormalities
- Other intercurrent illnesses including acute exacerbations of COPD, major surgery, or gastrointestinal problems
- Use of prohibited treatment
- Any other protocol deviation that results in a significant risk to the participant's safety

After a laboratory abnormality leading to a delay of dosing normalizes sufficiently, study treatment may resume at the discretion of the Site Investigator in consultation with the Study PI as needed. Similarly, study treatment may resume after the medication leading to suspension of dosing is discontinued. A decision to discontinue study treatment and/or to reinstitute study treatment should be conveyed to the Study PI and the DCC. The Investigator may suspend study treatment at any time, without consultation with the Study PI if the urgency of the situation requires immediate action and if this is determined to be in the participant's best interest. However, the Study PI and DCC should be contacted as soon as possible in any case of study treatment discontinuation.

### 8.1.2. Re-challenge

Resumption of study treatment after temporary discontinuation should always be discussed with the DCC and study PI.

Re-challenge should be performed one time only if the study medication was held due to AST or ALT  $\geq 3x$  ULN. Re-challenge should only occur after the ALT or AST return to pretreatment baseline value.

In the specific case of liver tests meeting the study treatment discontinuation criteria in [Section 8.1](#), no re-challenge is permitted.

## 8.2. Discontinuation From the Study

The Investigator should consider the following when withdrawing a participant from the study:

- A participant may withdraw from the study at any time at his/her own request, or may be withdrawn at any time at the discretion of the Investigator for safety, behavioral, or administrative reasons.
- If the participant withdraws consent for disclosure of future information, the DCC may retain and continue to use any data collected before such the withdrawal of consent.
- If a participant withdraws from the study, he/she may request destruction of any samples taken and not tested, and the Investigator must document this in the site study records and notify the DCC.

## 8.3. Lost to Follow-up

A participant will be considered lost to follow-up if he/she repeatedly fails to return for scheduled visits and is unable to be contacted by the study site.

The following actions must be taken if a participant fails to return to the clinic for a required study visit:

- The site must attempt to contact the participant and reschedule the missed visit as soon as possible and counsel the participant on the importance of maintaining the assigned visit schedule and ascertain whether or not the participant wishes to and/or should continue in the study.
- In cases in which the participant is deemed lost to follow-up, the Investigator or designee must make every effort to regain contact with the participant (where possible, 3 telephone calls and mail a certified letter to the participant's last known mailing address. These contact attempts should be documented in the participant's file.
- Should the participant continue to be unreachable, he/she will be considered to have withdrawn from the study with a primary reason of lost to follow-up.

## **9. Study Assessments and Procedures**

- Study procedures and their timing are summarized in the SOA.
- Adherence to the study design requirements, including those specified in the SOA, is essential and required for study conduct.
- All screening evaluations must be completed and reviewed to confirm that potential participants meet all eligibility criteria. The Investigator will maintain a screening log to record details of all participants screened and to confirm eligibility or record reasons for screening failure, as applicable.
- .
- Sample handling: Routine bloodwork and laboratory measurements used for safety monitoring and eligibility assessment (CMP, coagulation measurements, CBC, pregnancy testing, etc.) will be processed and measured using local laboratory. Samples (blood, sputum, BAL) used for PK or biomarker assessment will undergo initial processing at the local site but will be shipped to a central lab ([name]) at UAB for curation and analysis. The procedure is detailed in the MOP.
- Repeat or unscheduled samples may be taken for safety reasons or for technical issues with the samples.
- Biomarker samples (blood, sputum, and BAL) will be stored for up to 60 months after the end of the study.

## 9.1. Key Screening Assessments

### FIB-4 Score

The FIB-4 test combines age with 3 standard biochemical values (platelets, ALT, and AST) as a non-invasive test to assess fibrosis and enable exclusion of participants who may be at greater risk of liver AEs (<https://www.mdcalc.com/fibrosis-4-fib-4-index-liver-fibrosis>). The following formula will be used:

$$\text{FIB-4} = \frac{\text{Age (years)} \times \text{AST Level (U/L)}}{\text{Platelet Count (10}^9\text{/L)} \times \sqrt{\text{ALT (U/L)}}}$$

Using a cut-off value of 1.45, a FIB-4 score <1.45 has been shown to have a negative predictive value of 90% for advanced fibrosis. In contrast, a FIB-4 >3.25 would have a 97% specificity and a positive predictive value of 65% for advanced fibrosis. FIB-4 index has been shown to be superior to other scoring systems for differentiating between advanced and mild fibrosis.

## 9.2. Efficacy Assessments

### 9.2.1. Blood, Sputum, and Bronchoalveolar Lavage Biomarkers

#### Blood

Blood will be collected as per the SOA, and samples will be collected and processed as described by the MOP.

#### Sputum

Sputum will be collected from induced samples (refer to the MOP for processing details). Sputum induction will not be undertaken if the baseline FEV1 for the procedure is less than 1 L. Further details of sputum induction will be included in the MOP. Sputum induction is considered an aerosol generating procedure (AGP) and sites should use local guidance on conducting AGP as part of clinical research in the COVID-19 era.

#### Bronchoalveolar Lavage (BAL)

BAL will be collected in the subset of participants who agree to participate in the bronchoscopy sub-study. Samples will be collected at two time points as per the SOA, and samples will be collected and processed as described by the MOP. Bronchoscopy and BAL is considered an aerosol generating procedure (AGP) and sites should use local guidance on conducting AGP as part of clinical research in the COVID-19 era.

Blood, sputum, and BAL efficacy biomarkers (see [Table](#) below) will be taken at the time points as detailed in the SoA to evaluate their association with the observed mechanism of action responses to neutrophil elastase inhibition, including response of neutrophil elastase activity, inflammation, and lung damage to alvelestat (MPH966).

The samples will be collected and processed as described in the MOP.

Samples may be stored for a maximum of 60 months following the end of study at a facility selected by the Sponsor to enable further analysis of biomarker responses to alvelestat (MPH966).

### Biomarkers of Efficacy Collected in Blood and Sputum

Biomarker	Blood	Sputum	BAL
Neutrophil Elastase Related Biomarkers			
Desmosine/Isodesmosine	X	X	X
A $\alpha$ -Val 	X	X	X
NE	X	X	X
EL-NE	X	X	X
Proteinase 3	X		X
Cathepsin B	X		X
Lung Damage Biomarkers			
EL-CG	X		X
EL-P3	X		X
PGP	X	X	X
C6M	X		X
C1M	X		X
PRO-C6	X		X
Inflammatory Biomarkers			
Hs-CRP	X		
IL-6	X	X	X
IL-8	X	X	X
RANTES	X	X	
IL-1 $\beta$	X	X	
Fibrinogen	X		
LTB-4		X	X
MMPs	X	X	X
MPO	X	X	X

In addition, samples will be stored and analysis may be performed on additional biomarker variants thought to play a role in neutrophil elastase–induced lung damage to evaluate their association with observed neutrophil activation responses to alvelestat (MPH966).

#### 9.2.2. SGRQ-C

The St. George's Respiratory Questionnaire (SGRQ-C) will be administered at time points as detailed in the SoA. This is a questionnaire that measures health impairment in patients with COPD. It consists of 3 parts: a symptom score, an activity score, and an impact score. A total score is also produced.

#### 9.2.3. COPD Assessment Test (CAT)

The CAT is an 8 item questionnaire used to report health status in COPD. It will be administered at time points as shown in the SOA.

#### 9.2.4. Modified Medical Research Council (MMRC)

The MMRC will be administered at time points as detailed in the SoA and is used to measure dyspnea on a 5-point scale.

### **9.2.5. San Diego Breath Questionnaire (SOBQ)**

The SOBQ assesses patient reported dyspnea. The SOBQ will be administered at time points as detailed in the SoA.

### **9.2.6. Pulmonary Function Testing/Spirometry**

Pulmonary function testing (FEV1, FVC, FEV1/FVC, and maximal mid-expiratory flow) will be performed at the times specified in the SoA according to ATS guidelines. Further details on the spirometry procedure can be found in the Specific MOP. Spirometry is considered an aerosol generating procedure (AGP) and sites should use local guidance on conducting AGP as part of clinical research in the COVID-19 era.

### **9.2.7. Daily respiratory symptom scores and peak flow by electronic diary**

Participants will complete a 2 week baseline period of diary entries after screening and prior to randomization to establish a baseline. Participants will then complete the daily diary throughout the 16 week treatment period. Study sites will review diary entries at each clinic visit to confirm compliance and query possible adverse events.

## **9.3. Safety Assessments**

Planned time points for all safety assessments are provided in the SoA.

### **9.3.1. Physical Examinations**

- A complete physical examination will include, at a minimum, assessments of the cardiovascular, respiratory, gastrointestinal, integumentary, and neurological systems. Height and weight will also be measured and recorded.
- A brief physical examination will include, at a minimum, assessments of the lungs, heart, abdomen, and skin.
- Investigators should pay special attention to clinical signs related to previous serious illnesses.

### **9.3.2. Vital Signs**

Vital signs will be measured in a semi-supine position after 5 minutes of rest and will include temperature, systolic and diastolic blood pressure, heart rate, respiratory rate, and pulse oximetry.

- Oral or tympanic temperature.
- Blood pressure and pulse measurements will be assessed with a completely automated device. Manual techniques will be used only if an automated device is not available.
- Blood pressure and pulse measurements should be preceded by at least 5 minutes of rest for the participant in a quiet setting without distractions (e.g., television, cell phones).
- Pulse oximetry will be measured using a sensor placed on the participant's fingertip or earlobe. Oxygen saturation (SpO2) will be recorded.

## Electrocardiograms

- 12-lead ECG will be obtained as outlined in the SoA using an ECG machine that automatically calculates the heart rate and measures PR, QRS, QT, and QTc intervals. Refer to [Section 8.1](#) for QTc withdrawal criteria and additional QTc readings that may be necessary.
- Single ECGs will be performed at all scheduled time points, with the exception of when a change from baseline occurs that meets drug discontinuation criteria ([Section 8.1](#)). In this situation, a triplicate measurement is required to confirm the finding and for discontinuation decisions.
- When a triplicate ECG is required, 3 consecutive ECG tracings should be taken in a 30-minute period with at least 5 minutes between each ECG.
- QTc value will be calculated using the Fridericia formula ( $QTc=QT/3\sqrt{RR}$ ).

### 9.3.3. Clinical Safety Laboratory Assessments

- Refer to [Appendix 2](#) for the list of clinical laboratory tests to be performed and to the SOA for the timing and frequency.
- The Investigator must review the laboratory report, document this review, and record any clinically relevant changes occurring during the study in the AE section of the CRF. The laboratory reports must be filed with the source documents. Clinically significant abnormal laboratory findings are those that are not associated with the underlying disease, unless judged by the Investigator to be more severe than expected for the participant's condition.
- All laboratory tests with values considered clinically significantly abnormal during participation in the study or within 28 days after the last dose of study treatment should be repeated until the values return to normal or baseline, with a frequency based on the judgement of the Site Investigator. If such values do not return to normal/baseline within a period of time judged reasonable by the Investigator, the etiology should be identified and the DCC notified.

The monitoring schedule proposed for a case of acute liver function abnormalities or worsening of a liver function abnormality is reported is listed in [Section 8.1](#) (Liver Test Abnormalities).

- Clinically significant liver function abnormalities should be reported as an AE/AESI.
- All protocol-required laboratory assessments, as defined in [Appendix 2](#), must be conducted in accordance with the MOP and the SOA.

### 9.3.4. Data Safety Monitoring Board

Safety will be regularly reviewed by an independent DSMB who will have the option to unblind masked group data as necessary.

At any time, the DSMB may choose to recommend pausing, modifying, or stopping enrolment.

Full details of composition, operational aspects, and data to be reviewed and recommendations to be made by the DSMB will be described in the DSMB charter.

## 9.4. Adverse Events

The definitions of an AE, SAE, SUSAR, and UP can be found in [Appendix 4](#).

An AE will be reported by the participant (or, when appropriate, by a caregiver, surrogate, or the participant's legally authorized representative).

The Investigator and any designees are responsible for detecting, documenting, and reporting events that meet the definition of an AE or SAE and remain responsible for following AEs that are serious, considered related to the study treatment or the study, or that caused the participant to discontinue the study treatment (see [Section 8.1](#)).

### 9.4.1. Time Period and Frequency for Collecting AE and SAE Information

All AEs and SAEs will be collected from the signing of the ICF until the follow-up visit at the time points specified in the SoA.

All SAEs will be recorded and reported to the DCC within 24 hours, as indicated in [Appendix 4](#).

The method of recording, evaluating, and assessing causality of AEs and SAEs and the procedures for completing and transmitting SAE reports are provided in [Appendix 4](#).

### 9.4.2. Follow-up of an AE and/or SAE

After the initial AE/SAE report, the Investigator is required to proactively follow each participant at subsequent visits/contacts. All SAEs and non-serious AESIs (as defined in [Section 9.4.3](#)), will be followed until resolution, until stabilization, until the event is otherwise explained, or until the participant is lost to follow-up (as defined in [Section 8.3](#)). Further information on follow-up procedures is given in [Appendix 4](#).

### 9.4.3. Adverse Events of Special Interest

Some AEs, regardless of their severity or outcome, will be expedited due to the relevance for subject safety or study treatment safety profile. These events should be reported to the DCC within 24 hours, as indicated in [Appendix 4](#). The AESIs for alvelestat (MPH966) are:

- Liver function abnormalities defined as:
  - a) Any occurrence of (i) ALT or AST elevations  $>5 \times \text{ULN}$  or (ii) ALT or AST  $>3 \times \text{ULN}$  and total bilirubin  $>2 \times \text{ULN}$  or INR  $>1.5$  or the appearance of worsening fatigue, nausea, vomiting, RUQ pain/tenderness, fever, rash, or eosinophilia.
  - b) Any occurrence of  $<5 \times \text{ULN}$  or ALT or AST  $<3 \times \text{ULN}$  and total bilirubin  $<2 \times \text{ULN}$  where the tests have been repeated within 48 to 72 hours and the elevation confirmed on at least 2 separate occasions.

For participant safety and to ensure that the hepatotoxic potential of the study treatment to be determined, a standardized procedure for identification, monitoring, and evaluation of liver events must be followed as outlined in [Section 9.3.3](#) and [Section 8.1](#).

- ECG/Cardiac Events

If a study subject experiences any of the following cardiovascular events, the event should be reported immediately as an AESI and the study treatment discontinued:

- a) Absolute QTcF >500 ms or >60 ms increase from baseline.
- b) Any clinically significant cardiac abnormality on ECG.

- Infection

Any new infection that requires the use of systemic antimicrobial treatment (antibiotics, anti-viral, anti-fungal, or anti-mycobacterial) should be investigated with clinically relevant diagnostic tests.

Acute exacerbations of COPD are considered AESI.

- Neutropenia

- a) Absolute neutrophil count less than or equal to  $1.0 \times 10^9/L$  on 2 consecutive repeat tests within 48 to 72 hours.

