#### Liver Test Abnormalities

The following monitoring schedule is proposed when a case of acute liver function abnormalities or worsening of a liver function abnormality is reported:

- If ALT or AST are between 1.5 to 3 × ULN, regular monitoring (every 2 weeks at a minimum) is required until event resolution and patient can **continue on study treatment** during this period.
- If ALT or AST are  $\geq 3 \times$  ULN, repeat the test within 48 to 72 hours and the **study treatment will be temporarily discontinued** while awaiting repeat tests results; if the repeat tests is again  $\geq 3 \times$  ULN or  $\geq 2 \times$  pre-treatment level, testing needs to be repeated at least twice weekly until event resolution or a return to baseline value while the study treatment is **withheld**.
- If AST or ALT are  $\geq 5x$  ULN, a repeat value should be obtained within 24-48 hours. If the repeat ALT and AST values is  $\geq 5 \times$  ULN, the drug should be discontinued and the patient followed until the laboratory values normalize or stabilize, in addition to initiating potential (Drug Induced Liver Injury) DILI evaluation.

Discontinue Alvelestat (MPH966) for the following hepatic adverse events:

- Regardless of the magnitude of the transaminase elevation, if the bilirubin is elevated (any level) in addition to the presence of signs and symptom(s) such as rash, eosinophilia, nausea, vomiting, or right upper quadrant pain,
- INR  $\geq 1.5$  and TB  $\geq 2x$  ULN, irrespective of the magnitude of ALT or AST elevation.
- TB elevation  $\geq 2x$  ULN, and ALP  $\geq 2x$  ULN for cholestatic liver injury.

For each scenario, initiate potential DILI evaluation for alternative etiologies and obtain a hepatology consult. Liver biopsy should be considered for DILI. The complete liver profile including PT/INR must be repeated within 48-72 hours after first abnormal value is obtained. Follow the patient until laboratory parameters stabilize or normalize. Study medication can be restarted only if an alternative etiology is “definitively” identified and liver tests have returned to baseline. Testing for alternative etiologies can include serology tests (hepatitis A, hepatitis B, hepatitis C, Cytomegalovirus (CMV), Epstein-Barr Virus (EBV), Herpes Simplex Virus (HSV), varicella zoster virus (VZV), parvovirus, toxoplasmosis), imaging, and pathology assessments (creatinine phosphokinase, clotting) as appropriate to the clinical situation.

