### Protocol-Required Safety Laboratory Assessments

Laboratory Assessments	Parameters			
Hematology	Platelet Count RBC Count Hemoglobin Hematocrit	MCV MCH %Reticulocytes	WBC count with differential (% and absolute counts): Neutrophils Lymphocytes Monocytes Eosinophils Basophils	Prothrombin Time (PT) Partial prothromboplastin time (PTT) International normalized ratio (INR)
Clinical Chemistry 	Blood urea nitrogen	Potassium	AST/Serum glutamic-oxaloacetic transaminase (SGOT)	Total and direct bilirubin
	Creatinine and estimated glomerular filtration rate clearance	Sodium	ALT/Serum glutamic-pyruvic transaminase (SGPT)	Total protein
	Alkaline phosphatase	Calcium		
Other Screening Tests	
 
• Urine pregnancy test during the study (as needed for women of childbearing potential)
 
• Serum human chorionic gonadotropin pregnancy test (as needed for women of childbearing potential)
 
• Alpha-1 antitrypsin blood protein levels
 
• Serology (HIV antibody, hepatitis B surface antigen and hepatitis B antibody, and hepatitis C virus antibody)
 
• All study-required laboratory assessments will be performed at the local laboratory, with the exceptions of the samples (blood, sputum, BAL) that will be sent to a central laboratory for curation and analysis.
 
• The results of each test must be entered into the CRF as guided by the CRF Completion Guidelines.
 
			
 Details of liver chemistry stopping criteria and required actions and follow-up assessments after liver stopping or monitoring event are given in Section 8.1 . All events of ALT $\geq 3 \times$ ULN and bilirubin $\geq 2 \times$ ULN (>35% direct bilirubin) or ALT $\geq 3 \times$ ULN and INR >1.5, if INR is measured, which may indicate severe liver injury (possible Hy's Law), must be reported as an SAE.  Local urine testing will be standard.				

Investigators must document their review of each laboratory safety report.

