# 9.3 Safety Outcomes

### 9.3.1 Primary Safety Outcomes

The primary safety outcomes of interest are (1) numbers and % of subjects who experience at least 1 treatment-emergent adverse event and (2) adverse events of special interest (liver function abnormalities, corrected QT interval/cardiac, infections, and neutropenia). AEs will be coded using the Medical Dictionary for Regulatory Activities (MedDRA). Summaries will be by system organ class and preferred term. We will also present data separately by augmentation.

Treatment-emergent AEs (TEAEs) are defined as any AE occurring on or after the first dose of study medication. Listing will be sorted by treatment arm, subject ID, chronologically (start and end dates) and then alphabetically by SOC, PT and then verbatim description. The listing will include all the distinct levels of SOC, PT and the verbatim Investigator description reported in the study. A flag per subject will be included to indicate whether the patient received COVID-19 vaccination. If a participant experiences the same preferred term multiple times, the event will be counted only once overall and by the greatest severity. The frequency and incidence of TEAEs will be presented by system organ class and preferred term for each treatment group (number and percentage of participants experiencing at least 1 AE per preferred term as well as the number of observed events per preferred term). Separate tables will be presented by severity and by relationship to study drug. All AEs will be presented in a comprehensive listing

including participant number, treatment regimen, day of onset, severity, seriousness, action taken, outcome, relationship to treatment, onset/stop, and duration. Details of SAEs and AEs leading to withdrawal will be listed separately.

The frequency and incidence of adverse events of acute exacerbations of COPD will be presented (number and percentage of participants experiencing at least 1 AE per preferred term as well as the number of observed events per preferred term) and overall. Events that started after treatment initiation (TEAEs) up until Week 12 will only be presented, meaning that events commencing after the end of treatment and during the safety follow up period will not be summarized.

AESIs, including liver function abnormalities, ECG/cardiac events, infections, and neutropenia, will be tabulated and summarized by treatment group and overall.

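### The liver AESI definition leaves out some of the hepatic stops in Protocol Section 8.1, most clearly the bilirubin/ALP stop, and its wording does not give a single liver AESI count

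*Protocol*

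**What the plan says.** Protocol Section 4 gives the primary safety endpoint two parts: participants with at least one treatment-emergent AE, and AESIs, of which liver function abnormalities are one.

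Protocol Section 9.4.3 defines the liver AESI by a list and requires a report to the DCC within 24 hours.
- Part (a)(i): "Any occurrence of (i) ALT or AST elevations" above 5× ULN.
- Part (a)(ii): ALT or AST above 3× ULN and total bilirubin (TB) above 2× ULN or INR above 1.5 "or the appearance of worsening fatigue, nausea, vomiting, RUQ pain/tenderness, fever, rash, or eosinophilia". There are no brackets.
- Part (b): a result below 5× ULN with no analyte named, or ALT or AST below 3× ULN with TB below 2× ULN, "where the tests have been repeated within 48 to 72 hours and the elevation confirmed on at least 2 separate occasions".
- ALP does not appear.

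Protocol Section 8.1 contains two lists that matter here.
- The mandatory list: ALT/AST above 5× ULN twice, or above 3× ULN with TB above 2× ULN, with INR above 1.5, or with symptoms. The 3× condition is repeated in each of those three bullets.
- Three further stops, which the section itself calls hepatic adverse events. The first begins "Regardless of the magnitude of the transaminase elevation, if the bilirubin is elevated (any level") and also requires signs or symptoms. The second is INR at least 1.5 with TB at least 2× ULN, "irrespective of the magnitude of ALT or AST elevation". The third is TB at least 2× ULN with ALP at least 2× "ULN for cholestatic liver injury".

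Sections 8.1 and 9.3.3 both say that clinically significant liver abnormalities are to be reported as an AE/AESI, without saying which. Footnote 1 in Appendix 2 describes ALT at least 3× ULN with raised bilirubin or INR as events "which may indicate severe liver injury (possible Hy's Law), must be reported as an SAE"; it does not mention AST.

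SAP 9.3.1 states: "AESIs, including liver function abnormalities, ECG/cardiac events, infections, and neutropenia, will be tabulated and summarized by treatment group and overall". It gives no liver rule of its own.

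**The concern.** Liver injury is a named risk of the drug, and Protocol Section 5.8 gives it as the reason for making liver abnormalities an AESI. The any-AE component counts a cholestatic stop the same as a mild headache; the AESI component is what isolates liver harm. If an event that Section 8.1 treats as serious enough to stop drug lies outside the liver AESI, the liver row of the AESI table can be short by that event, and the 24-hour AESI report is not triggered.

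The wording adds a second difficulty. Neither (a)(ii) nor (b) can be programmed, or applied at a site, in only one way. Two careful people could produce different liver AESI counts from the same data, and the SAP does not choose between them.

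**Working it through.** There is no stated figure to reproduce; the check is logical.

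**Inputs.** The two lists in Section 8.1, the AESI definition in Section 9.4.3 and footnote 1 of Appendix 2 were written as conditions on multiples of ULN. ALT and AST were taken as one value, and repeat tests were assumed to confirm. Readings tested:
- (a) grouped: ALT/AST above 3× ULN is needed throughout (ii), as in the mandatory list.
- (a) ungrouped: INR above 1.5, or a listed symptom, is enough alone.
- (b) strict: ALT/AST above ULN and below 3×, with TB below 2×.
- (b) loose: any ALT/AST above ULN and below 5×.

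**Grid.** ALT/AST 1, 2, 2.9, 3, 3.5, 4.9, 5, 6; TB 0.8, 1.5, 2, 2.5; INR 1.0, 1.5, 1.6; ALP 1, 2, 3; symptoms no/yes. This gives 8×4×3×3×2 = 576 profiles.

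**Profiles that meet a stop but miss the AESI:**

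| Stop in Section 8.1 | Meeting it | (a) grouped | (a) ungrouped | Grouped + strict (b) | Grouped + loose (b) | Ungrouped + loose (b) |
|---|---|---|---|---|---|---|
| Mandatory list | 234 | 0 | 0 | 0 | 0 | 0 |
| Bilirubin + symptoms | 216 | 108 | 0 | 90 | 27 | 0 |
| INR + TB | 192 | 105 | 33 | 105 | 27 | 9 |
| TB + ALP | 192 | 108 | 44 | 108 | 28 | 12 |

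These are grid cells, not patient frequencies. They show whether a gap exists, not how often it would occur.

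**Hand check of the last row.**
- Meeting the stop: 8 (ALT/AST) × 2 (TB) × 3 (INR) × 2 (ALP) × 2 (symptoms) = 192.
- Missed by (a) grouped: ALT/AST at or below 3× gives 4×2×3×2×2 = 96. ALT/AST of 3.5, 4.9 or 5 with TB exactly 2, INR at most 1.5 and no symptoms gives 3×1×2×2×1 = 12. Total 96 + 12 = 108.
- Missed by the broadest reading: 8 at ALT/AST 1× (2 TB × 2 INR × 2 ALP) and 4 at exactly 5× with TB exactly 2 (2 INR × 2 ALP). Total 12. The latter four arise because (a)(i) starts above 5× and (b) ends below 5×.

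All 33 INR + TB misses under the ungrouped reading have INR exactly 1.5: the stop uses at least 1.5, the AESI above 1.5.

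**Single profiles.**
- ALT/AST 1×, TB 2.5×, ALP 3×, INR 1.0, no symptoms: a stop; not an AESI under any reading above.
- ALT/AST 1×, TB 2.5×, INR 1.6: a stop; outside (a) grouped, inside (a) ungrouped.
- ALT/AST 2×, TB 1.5×, nausea: a stop; outside (a) grouped, inside (b) if confirmed.
- AST 4×, ALT 2.5×, TB 2.5×: a mandatory stop (AST above 3×, TB above 2×) and an AESI. The Appendix 2 footnote needs ALT at least 3×, so it does not make this case an SAE.

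**Size of one event.** 66 randomised 1:1 gives 33 per arm; 1/33 = 3.0 percentage points.

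**The case against.** The case on the other side has real weight.

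- A reader might infer that these participants drop out of the primary safety endpoint. They do not. Section 8.1 calls the three stops adverse events, so with onset on or after first dose they count in the first component. SAP 9.3.1 lists AEs leading to withdrawal separately, the SAP plans a table of treatment-emergent AEs leading to permanent withdrawal of study drug, and laboratory values are summarised by visit.
- A reader might infer that Section 8.1 as a whole is uncaptured. Part (a) covers the mandatory list completely.
- A reader might infer that the participants concerned are stopped for good. The documents leave that open: Section 8.1 allows restart if another cause is definitively identified and liver tests return to baseline, while Section 8.1.2 bars re-challenge when the Section 8.1 liver criteria are met. Those passages need reconciling in their own right.
- Under-counting and over-counting cannot both be claimed from one reading. Grouped, (a)(ii) misses the INR/TB and bilirubin-plus-symptom stops at low transaminases; ungrouped, it takes in nausea alone. The mandatory list points to the grouped reading.
- The first two stops speak of the magnitude of a transaminase elevation, so they may presuppose some elevation. A confirmed mild one could then enter through a loose (b).
- Section 9.4.3 cross-refers to Sections 9.3.3 and 8.1, which carry the AE/AESI sentence. Section 8.1.1 requires contact with the Study PI and DCC as soon as possible after any study treatment discontinuation.
- The Appendix 2 footnote adds an SAE trigger; it does not define SAEs. An AST-driven case can still be serious on judgement under Appendix 4, and it already carries the 24-hour AESI report.
- Few events are likely. Protocol Sections 5.7 and 5.8 report five liver-related AEs and no liver SAE or AESI in the companion AATD study, and no liver abnormalities so far in this one. The safety analysis is descriptive.

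All of this limits the consequence, but it does not close the gap. AE/AESI does not say which label applies, and prompt contact with the DCC is not an entry in the AESI table. A loose (b) is a poor rescue: it sets no lower bound, while eligibility admits ALT and AST up to 1.5× ULN, so small stable elevations would need the general AE definition to keep them out.

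**Conclusion.** The point holds in a limited form. The liver AESI list covers the mandatory stopping list but not all of the three additional hepatic stops. The firm case is the TB/ALP stop with near-normal transaminases. It lies outside every reading that takes the unnamed analyte in (b) to be ALT or AST; only by letting that analyte be bilirubin or ALP could it be brought in, and the text gives no support for this. The INR/TB and bilirubin-plus-symptom stops lie outside part (a) on the grouping that Section 8.1 itself uses, with partial cover from a loose (b).

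The effect is confined to the AESI component of the primary safety endpoint and its 24-hour report. Each misclassified event moves that component by 3.0 percentage points in an arm of 33. The number of such events is unknown and could be zero. The ALT-only footnote is a separate, smaller inconsistency. It is still worth correcting, because the AESI table is where liver harm is meant to be visible by arm. No view is taken on which clinical threshold is right.

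**What to change.** Reconcile Section 9.4.3 with both lists in Section 8.1, with the AE/AESI sentence in Sections 8.1 and 9.3.3, and with footnote 1 of Appendix 2. For counting and reporting only:

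1. Add to the liver AESI any event that meets a hepatic discontinuation criterion of Section 8.1, naming the lists meant.
2. Bracket (a)(ii) so that ALT or AST above 3× ULN governs bilirubin, INR and symptoms alike, as in the mandatory list.
3. In (b), name the analyte for the 5× limb, give a lower bound, and state what happens at exactly 5×.
4. Have the sponsor decide whether the Appendix 2 footnote means ALT, or ALT or AST, and word it accordingly.
5. Put one liver AESI derivation rule in SAP 9.3.1, using laboratory and discontinuation data, and fix it before unblinding.

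The cost is one protocol clarification and one SAP rule. ALT, AST, ALP, bilirubin and INR are already in the Appendix 2 laboratory panel. The downside is a few more expedited reports. No stopping threshold is changed or proposed.
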